2.2 Stage 2: Application of the sustainable-psycho-nutritional intervention program

2.2.1 Participants

Once the intervention program has been designed, it will be applied to a sample of Mexican young adults from the south of Jalisco, randomly divided into two groups: an experimental group (n=50) and a control group (n=50). This is based on recommendations for group designs in behavior modification programs (38). The sample size is according to the minimum suggested for nutritional interventions (39,40), and taking into account the possible desertion of the participants during the intervention, which can amount to more than 50% of the initial sample (41). We will include a population between 18 and 35 years old, with Body Mass Index (BMI) values from 18.5 to 40, with or without risk factors for the development of chronic diseases, but without diagnosis with previous pharmacological treatment. The inclusion, exclusion, and elimination criteria are detailed in Supplementary Material 2 in Table SM2.1. Also, for being included in the study cut-off points to identify inadequate consumption and physical activity were established (Table SM2.2). The population will be invited to participate through social networks and posters at strategic points, such as Universities, gyms, and the downtown city. Young adults were selected as the population for this study since they are already considered adults who make autonomous food decisions, but at the same time, their young age makes them susceptible to behavioral modification. In addition, they represent parents or future parents, as well as the active population of Mexico, so providing nutritional-sustainable education to these people could generate long-term benefits for their health and that of their families (21,42,43).

2.2.2 Procedure

Participants will be evaluated following the nutritional care process model (44). The first evaluation will be performed at the beginning of the intervention at baseline, and according to individual requirements, the behavioral objectives will be individually adapted and will be addressed for 7 weeks, considering 2 objectives per week, thus providing 2 weekly educational workshops. Also, personalized food plans will be prescribed, according to the linear programming optimization (29,30) performed at MATLAB®.

After 7 weeks of educational and nutritional intervention, at week 8, the experimental population will be divided into two sub-groups, where one group will stop being intervened completely (n = 25), and another will continue to receive messages through the mobile application (n = 25) for 8 weeks. Finally, at week 15, a final evaluation will be carried out. The study design is shown in Figure 2. Participants will be evaluated in the regard of Anthropometric, Biochemical, Clinical, Dietetics, Environmental, Socioeconomic level and cultural aspects,

Nutritional-sustainable knowledge, Behavioral aspects, and Physical activity (ABCD-ESNBP). These aspects will be evaluated according to the nutritional care process model, thus identifying the problem of the population, establishing the etiology, and stating the signs and symptoms (44).

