2.3.4 Statistical analyses

The distribution of the data will be analyzed with the Kolmogorov Smirnov test. Descriptive analysis will be performed, including means, standard deviations, and medians. Next, the effects of the program on the selected variables will be assessed by comparing them between evaluations and between groups with t-student tests for paired and unpaired data, respectively, if a normal distribution is found. For no normally distributed data, the Wilcoxon test (repetitive measures) and the U de Mann Whitney test (independent groups) will be used. For no categorical variables, the chi-squared test will be used. Correlation analyses will also be performed, considering Pearson correlation for normally distributed data and Spearman correlations for no normally distributed data. Likewise, simple, and multiple linear regression models will be carried out, as well as binary logistic regression analysis, to identify relationships and risks between variables. Statistical analysis will be performed at STATA V12® program.

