Note: this table will be updated according to the linear optimization programming.

Supplementary Material 2. Inclusion, exclusion, and elimination criteria

Table SM2.1. Inclusion, exclusion, and elimination criteria

Study Criteria		
Inclusion	Exclusion	Elimination
Being between 18 and 35 years old	Not signing the informed consent	Not completing the questionnaires
Being Mexican	Not accepting to donate blood and/or stool samples	Do not allow the extraction of blood and / or delivery of stool sample
Reside in the South of Jalisco for at least 1 year	Not being able to stand up to take anthropometric data	Failure to complete the 7-week intervention or 7-week follow-up
Levels of physical activity below what is recommended and what is established as a criterion for inclusion in the study (Table SM2)	Perform levels of physical activity above the minimum established as criteria for inclusion in the study (Table SM2)	
Consuming amounts of food below or above that established as criteria for inclusion in the study or in a lesser or greater frequency than recommended, according to the type of food (Table SM2)	Consume adequate levels of the foods to be promoted in the intervention program (Table SM2)	
Have a Smartphone	Being pregnant or lactating	
Not having consumed antibiotics at least 3 months before the intervention	Suffer from a chronic disease such as type 2 diabetes mellitus, arterial hypertension, dyslipidemia, under medication	
Have a BMI between 18.5 and 40	Suffering from an autoimmune disease such as type 1 diabetes, hypo or hyperthyroidism	
Not having a medical diagnosis of chronic disease under pharmacological treatment	Having a gastrointestinal disease such as Crohn's disease, ulcerative colitis, etc.	
Not having a medical diagnosis of gastrointestinal disease	Having used antibiotics less than 3 months ago	
	Taking antidepressant medications or corticosteroids	
	Consume probiotics or nutritional supplements, except protein powder	

Table SM2.2 Cut-off points to establish inadequate consumption and physical activity, to be included in the research

Physical activity	Inclusion criteria	
	Light	
	< 3 times per week	< 30 minutes per day
Type of physical activity		
Weekly frequency		
Minutes per day		
Food group	Consumption to be included in the study	Frequency of consumption to be included in the study
Mexican food and dishes	< 100 g p ⁻¹ d ⁻¹	< 7 times a week
Fruits	< 400 g p ⁻¹ d ⁻¹	< 7 times a week
Vegetables	< 400 g p ⁻¹ d ⁻¹	< 7 times a week

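### The week-8 sub-groups of 25 and 25 use up all 50 randomised to the experimental arm, so they assume no loss; at week 15 three groups exist, but no contrast is named and no baseline adjustment is described

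*Combined protocol and SAP*

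**What the plan says.** Section 2.2.1 has the sample "randomly divided into two groups: an experimental group (n=50) and a control group (n=50"). It says the size takes account of "possible desertion of the participants during the intervention, which can amount to more than 50% of the initial sample".

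Section 2.2.2 then describes seven weeks of intervention. For the week-8 split, the plan's wording is that "the experimental population will be divided into two sub-groups, where one group will stop being intervened completely (n = 25"). The remaining participants form the second sub-group, described as follows: "another will continue to receive messages through the mobile application (n = 25) for 8 weeks". It continues: "Finally, at week 15, a final evaluation will be carried out". For the overall layout it refers the reader on: "The study design is shown in Figure 2". That figure is not available in the text under review.

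Table SM2.1 in Supplementary Material 2 lists as an elimination criterion "Failure to complete the 7-week intervention or 7-week follow-up".

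Section 2.3.4 is a single general section for all evaluations. It assesses programme effects by "comparing them between evaluations and between groups with t-student tests for paired and unpaired data" when data are normal, and otherwise by the Wilcoxon and Mann-Whitney tests. A chi-squared test is also listed. Linear and logistic regression appear as well, but for finding relationships and risks among variables; neither a group term nor a baseline term is mentioned.

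The hypothesis in section 1 is about the programme as a whole: that it shifts eating behaviour and improves metabolic, microbiota, environmental and clinical outcomes.

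**The concern.** Two things in the plan do not fit together.

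First, the split happens after the seven weeks in which the plan itself expects people may leave, yet the sub-group sizes add up to everyone randomised. A reader who takes 25 per sub-group at face value will overrate what the follow-up comparison can show.

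Second, the split turns a two-group trial into a three-group trial (control, stopped, messages) by the week-15 evaluation. Four contrasts are then possible: whole experimental arm v control, messages v control, stopped v control, and messages v stopped. They answer different questions. None is tied to the hypothesis in section 1, so the choice could follow the data, and testing every pair inflates the false-positive rate. The effect analysis also makes no stated use of the baseline values that the trial collects anyway.

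If the sub-groups are not formed at random, staff or participant choice could explain a difference between them. The visible text does not settle this.

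**Working it through.** **Inputs.** From section 2.2.1: 50 experimental, 50 control, loss possibly above 50%. From section 2.2.2: sub-groups of 25 and 25 formed at week 8, final evaluation at week 15. From Table SM2.1: non-completers eliminated. Assumed, because the plan gives none: two-sided 5%, 80% power, outcome in SD units. In the main table the same proportion is lost from every group.

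**Step 1: reproduce the stated sizes.** With proportion d lost from the arm, size per sub-group = 50 × (1 − d) / 2.

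- d = 0: 50 / 2 = 25, the stated figure.
- d = 20%: 40 / 2 = 20.
- d = 50%: 25 / 2 = 12.5, so 12 and 13.
- d = 60%: 20 / 2 = 10.

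The stated 25 + 25 is reproduced only at d = 0. To have 25 + 25 left after 50% loss, the arm would need to start with 50 / (1 − 0.5) = 100.

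**Step 2: detectable difference.** Two-sample t test, noncentral t; approximately (1.96 + 0.84) × √(1/n₁ + 1/n₂), slightly larger once degrees of freedom are allowed for. Results in SD, with group sizes in brackets:

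| Loss | Whole arm v control | One sub-group v control | Messages v stopped |
|---|---|---|---|
| 0% | 0.57 (50 v 50) | 0.70 (25 v 50) | 0.81 (25 v 25) |
| 20% | 0.63 (40 v 40) | 0.78 (20 v 40) | 0.91 (20 v 20) |
| 50% | 0.81 (25 v 25) | 1.01 (12 v 25) | 1.17 (12 v 13) |
| 60% | 0.91 (20 v 20) | 1.12 (10 v 20) | 1.32 (10 v 10) |

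Equal loss is only one scenario. If the experimental arm alone lost 50%, whole arm v control would be 25 v 50, or 0.70 SD instead of 0.81, and one sub-group v control would be 12 v 50, or 0.92 instead of 1.01. Messages v stopped would not change.

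**Step 3: baseline adjustment.** Adjusting for a baseline value with correlation r multiplies the detectable difference by √(1 − r²). For 25 v 25 (0.81 SD), assumed r of 0.3, 0.5 and 0.7 gives 0.77, 0.70 and 0.58 SD.

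**Step 4: testing all pairs.** Three unadjusted pairwise t tests at 5% with no true differences: simulation gives a chance of about 12% of at least one false positive per outcome, at both 25/25/50 and 12/13/25. Independent tests would give 1 − 0.95³ = 14.3%; these share groups, so the figure is lower.

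**Step 5: what pooling the sub-groups costs.** In SD units, the standard error of the average of the two sub-groups minus control is √(¼/25 + ¼/25 + 1/50) = 0.200 with no loss. For messages minus control it is √(1/25 + 1/50) = 0.245. Let f be the stopped-group effect as a fraction of the messages effect. The pooled effect is (1 + f)/2 of the messages effect, so the two contrasts are equally sensitive when (1 + f)/2 = 0.200/0.245, giving f = 0.63. With 12/13/25 the standard errors are 0.283 and 0.351, and f = 0.61. Below roughly 61 to 63%, messages v control is the more sensitive contrast.

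**The case against.** The best defence has four parts.

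- **The 25s may be nominal.** Section 2.2.1 says the 50 per arm was chosen with desertion in mind, so 25 + 25 could be an even split of the enrolled arm. That is a possible reading, but section 2.2.2 places the split after seven weeks and gives no allowance for loss. The correction needed is small either way.
- **Figure 2 may fill gaps.** It could show how the split is made, and whether there is an evaluation at the end of the intervention. If there is one, only two groups exist then, two-sample tests suit the programme hypothesis, and the three-group difficulty is confined to follow-up. This stands, and it limits the point. It would not change the sub-group arithmetic or supply the baseline adjustment that section 2.3.4 does not describe.
- **Section 2.3.4 is general.** It is not a dedicated week-15 analysis, and that no adjustment is intended is inferred from silence. Two-sample tests can also be run pair by pair, and chi-squared can handle three groups. All true. What is missing is the choice of contrast, a rule for pooling the sub-groups, and error control.
- **The detectable differences depend on assumptions.** They do, and apart from baseline adjustment the fix does not improve them. They show the scale; they are not a sample-size verdict.

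A reader might go further and infer that the plan forecasts 50% loss, that the split is known to be non-random, or that the listed tests cannot be used at week 15. The documents support none of these: the loss is stated as a possibility, the method of splitting is not visible, and the tests can be used but are under-specified.

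**Conclusion.** The point holds in a limited form. The stated sub-group sizes are delivered only with zero loss over seven weeks; at the 50% loss that the plan allows for, they fall to 12 to 13. Messages v stopped could then detect only about 1.17 SD, against 0.81 SD with no loss, so it is exploratory in either case. At week 15 three groups exist, no contrast is tied to the programme hypothesis, and no baseline adjustment is described for the group comparison. Testing all pairs would carry about 12% family-wise error per outcome.

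The sizes follow directly from the plan's own numbers. The detectable differences and error rate rest on the assumed 5% level, 80% power and, in the main table, equal loss. Whether the split is random, and whether an end-of-intervention evaluation exists, stay open because Figure 2 is not shown. The changes should be made; confidence is moderate.

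**What to change.** 1. **Section 2.2.2, sizes.** State 25 per sub-group as the no-loss maximum, and give 20 at 20% loss, 12 to 13 at 50% and 10 at 60%. Label messages v stopped exploratory.
2. **Section 2.3.4, model.** For continuous outcomes, replace the unpaired test with a regression on group adjusted for the baseline value, with a three-level group term at week 15. Fix in advance which outcomes are transformed. If there is an evaluation at the end of the intervention, use the same adjusted comparison of experimental v control there.
3. **Contrasts.** Name whole experimental arm v control as the contrast for the programme hypothesis, because it keeps the original randomised comparison. Report messages v control, stopped v control and messages v stopped as secondary estimates with 95% confidence intervals and no significance claims.
4. **Non-completers.** Keep everyone with week-15 data in the group assigned, including those who did not complete the intervention, in place of elimination under Table SM2.1. If they are eliminated, describe the result as a comparison of completers.
5. **Forming the sub-groups.** Unless Figure 2 already provides for it, assign them at random at week 8 from a list prepared beforehand.
6. **Binary outcomes.** Analyse outcomes such as acanthosis nigricans as whole arm v control, with an exact or penalised method if events are few.

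**Cost.** Mainly wording, plus one randomisation list if it is not already planned; no extra participants, and regression is already among the listed methods. The stated sub-group size becomes less favourable. The whole-arm contrast averages two follow-up conditions, which is why the secondary estimates sit beside it. Section 2.4 records that ethics approval has been given, so a protocol amendment may be needed.

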2.2.3 Sustainable-psycho-nutritional indicators

The ABCD-ESNBP indicators will be included in a complete clinical history that will be uploaded to the mobile application (Supplementary Material 3) and will be evaluated as follows: A) Anthropometric: height with a Smartmet® stadiometer, weight, and body composition (percentage of body fat, muscle mass, visceral fat) with an Omron® bioimpedance scale (HBF-511T-E/HBF-511B-E), $BMI = \text{weight}/\text{height}^2$, waist and hip circumference using a Lufkin® metal tape measure. The assessment will be performed following the validated techniques of Suverza and Haua (45).

B) Biochemical: glucose and lipid profiles (TC, LDL-C, HDL-C, and TG) will be determined through blood samples that will be taken from the antecubital vein of each participant, following the protocol from the Mexican Health Secretary (46,47). Samples will be taken by specialists, after an overnight fast of 8 to 12 hours and will be centrifuged at 3500 rpm for 15 min to separate the serum. Samples will be aliquoted and stored at -20°C until the day of testing. Tourniquets, alcohol swabs, 10 mL syringes, and blood collection tubes will be required. Gut microbiota will also be analyzed, for which fecal samples will be collected in a sterile stool container using a sterile kit including gloves and a spatula that will be delivered to the participants. Once collected, the samples will be divided into aliquots and will be stored at -80 °C, following a method used for the Mexican population (4,48).

C) Clinical: a clinical history will be carried out, covering pathologies suffering, pathological family history, medicaments, and supplement use (Supplementary Material 3). Clinical signs of insulin resistance (acanthosis nigricans) will be evaluated by physical exploration, searching for hyperpigmentation and thickening of the skin with velvety, in visible flex areas (axilla, anterior ulnar area, and posterior and lateral region of the neck) (49). Signs of nutrient deficiencies or excess will also be evaluated in relation to hair, nails, mouth, tongue, edema, and mucous membranes appearance (45). Likewise, blood pressure will be evaluated with a Medstar® sphygmomanometer and following the Mexican normativity (50).

[figure not shown]

Figure 2. Study design for stage 2. Own elaboration.

D) Dietetics: caloric-nutritional intake will be assessed through 24-hour recalls and dietary records (51), and by a validated adapted Food Frequency Questionnaire (CFCA) (5,52). Diet quality will also be analyzed by an adapted version of the Mexican Diet Quality Index (ICDMx) (53). Participants will also be asked about food preparation, food shopping places, food allergies and intolerances, food preferences, and about following specific diets at the moment of the evaluation.

E) Environmental: dietary water footprint will be calculated using the Water Footprint Assessment method (54) in its version for Mexico's context (5). The water footprint of each food and food ingredients are going to be calculated. Also, water involved in cooking and food washing is going to be evaluated. Dietary carbon footprint is also going to be calculated using the Life Cycle Assessment method (7,55,56). Food system boundaries are going to be the impact of food production and processing on greenhouse gas emissions, as carried out by Fresán et al. (57). Corrections factors from converting cooked to uncooked food and peeled to unpeeled food are going to be applied. Both calculations are going to be performed in the Nutriecology® Software.

S) Socioeconomic level and cultural aspects: educational level, occupational level, and economic income are going to be evaluated according to classifications used for Mexico, which are detailed in Supplementary Material 3 (58). For this aspect, food prices are going to be investigated in fieldwork and in supermarket databases, in order to promote the consumption of accessible foods. Also, food culture related to celebrations and traditions is going to be investigated.

N) Nutritional-sustainable knowledge: it will be evaluated through a designed questionnaire (Supplementary Material 4), based on the psychological capacity presented in the COM-B model. It will include a series of questions for the evaluation of nutritional-sustainable knowledge, which will be related to the established behavioral objectives and will be based on manuals for the design of nutritional knowledge questionnaires and on questions on sustainable food consumption (59–62).

B) Behavioral aspects: all dimensions of the COM-B model will be assessed in a designed questionnaire based on Brain et al. (63) (Supplementary Material 4). The questions will be related to physical and psychological ability, automatic and reflexive motivation, and physical and social opportunity (14). Questions were adapted according to the context of sustainable diets (12): (1) Capacity: knowledge of sustainable nutrition, preparation skills food and preparation capacity; (2) Opportunity: time to eat and prepare food, access to food, and food storage; (3) Motivation: the desire to change eating habits, emotions involved in food consumption and habits that participants are willing to change.

P) Physical activity: the IPAQ questionnaire will be used, which is included in the clinical history shown in Supplementary Material 3. Besides the questionnaire, specific questions about physical activity type, frequency, intensity, and duration are going to be asked.

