2.3 Stage 3: Effects of the sustainable-psycho-nutritional intervention program

As the last stage of this protocol, the corresponding laboratory analyses, and statistical tests will be carried out.

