2.3.1 Metabolic biomarkers analysis

For the analysis of metabolic biomarkers, colorimetric enzymatic methods will be used using the Spinreact® S. A/S A. U (Girona, Spain) laboratory kits, for fasting glucose determination (Cat. No. 1001190), TC (Cat. No. 41022), LDL-C (Cat. No. BSIS51-E), HDL-C (Cat. No. BSIS37-E) and TG (Cat. No. 1001313) (47). The reference points for glucose values and lipid profiles will be taken from the regulations in force in Mexico (64,65).

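### If serum is assayed in stage 3, baseline samples are 14 to 15 weeks older than final ones, and the planned paired tests cannot separate a storage or assay-run shift from a programme effect

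*Combined protocol and SAP*

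**What the plan says.** **Storage.** Section 2.2.3, under the biochemical indicators, says of serum: "Samples will be aliquoted and stored at -20°C until the day of testing". No storage limit and no testing date are given. For stool, the same paragraph says "the samples will be divided into aliquots and will be stored at -80 °C".

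**When assays are run.** Section 2.3 opens stage 3 with: "As the last stage of this protocol, the corresponding laboratory analyses, and statistical tests will be carried out". The glucose and lipid kits are described inside that stage, in section 2.3.1: "For the analysis of metabolic biomarkers, colorimetric enzymatic methods will be used".

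**When blood is drawn.** Section 2.2.2 says "The first evaluation will be performed at the beginning of the intervention at baseline", and later "Finally, at week 15, a final evaluation will be carried out".

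**How effects are tested.** Section 2.3.4 assesses programme effects "by comparing them between evaluations and between groups with t-student tests for paired and unpaired data", with rank-based counterparts for non-normal data. It does not say which comparison takes precedence.

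**A possible pointer the other way.** Section 2.2.3 puts the indicators into a clinical history loaded to the app, and the initial assessment form in Supplementary Material 3 (Table SM3.1) has fields for fasting glucose and the lipids.

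**The concern.** Within one arm, every baseline sample comes from the first evaluation and every final sample from the last. If all are thawed and assayed in stage 3, length of storage coincides exactly with evaluation. If the visits are assayed separately, assay run coincides with evaluation. A shift in measured values from either source moves the mean within-person change, and that mean is what the paired test examines. No within-arm analysis can recover the difference, because there is no baseline serum with short storage and no final serum with long storage.

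The trial's metabolic hypotheses are at stake: section 1 expects glucose, TC, LDL-C and TG to fall and HDL-C to rise. The paired tests are one of two planned routes to a claim on these outcomes, and a shift could create a finding or hide one. Storage history cannot be corrected after the event, so the point has to be settled before baseline sampling.

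**Working it through.** The plan states no storage time, drift, significance level or power for these outcomes, so there is no figure to reproduce.

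**Step 1. Storage gap if all serum is assayed together in stage 3.** Gap = final sampling week − baseline sampling week.
- Final week is 15 and baseline is week 0 or 1 (section 2.2.2): 15 − 0 = 15, or 15 − 1 = 14 weeks.
- Cross-check by duration. The elimination criteria in Supplementary Material 2 (Table SM2.1) refer to "Failure to complete the 7-week intervention or 7-week follow-up": 7 + 7 = 14. Section 2.2.2 describes 8 weeks of messages after the first 7: 7 + 8 = 15.

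The gap is 14 to 15 weeks. If each visit were assayed after the same delay, the gap would be about 0, but the two visits would then fall in different runs.

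**Step 2. What a shift does to a paired test when the programme has no effect.** Let *d* be the mean shift from storage or run, in units of the SD of within-person change. The paired t statistic then follows a noncentral t with n − 1 degrees of freedom and noncentrality *d*·√n. The rejection rate is P(|T| > critical value) at an assumed two-sided 5% level; critical values are 2.064 (n=25) and 2.010 (n=50).

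The sizes come from the plan: 50 per arm (section 2.2.1) and 25 per experimental subgroup after week 8 (section 2.2.2). Section 2.2.1 also allows for loss of more than half the sample, so n=50 is the no-dropout case.

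| Assumed *d* | *d*·√25 | Significant, n=25 | *d*·√50 | Significant, n=50 |
|---|---|---|---|---|
| 0.05 | 0.25 | 5.7% | 0.354 | 6.4% |
| 0.1 | 0.50 | 7.7% | 0.707 | 10.7% |
| 0.2 | 1.00 | 16.1% | 1.414 | 28.4% |
| 0.3 | 1.50 | 30.2% | 2.121 | 54.8% |
| 0.5 | 2.50 | 67.0% | 3.536 | 93.4% |

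**Step 3. Direction.** Measured change = final − baseline. Suppose an analyte is lost in storage and baseline is stored longer. Baseline then reads too low and measured change is pushed upwards. For glucose, TC, LDL-C and TG, where a fall is expected, this masks the effect. For HDL-C, where a rise is expected, it mimics one. If an analyte reads higher after storage, the signs reverse.

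**Step 4. The between-arm comparison.** If both arms carry the same mean shift *d*, the expected difference in change is (effect + *d*) − *d* = effect. A simulation of 20,000 trials with 50 per arm and no true effect, using an unpaired t-test on change, gave false-positive rates of 5.1%, 5.4% and 5.0% at *d* = 0, 0.2 and 0.5. The test stays at about its nominal level.

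**The case against.** **No single assay date is stated.** This is correct, and the 14 to 15 weeks is conditional on assay in stage 3. The glucose and lipid fields on the initial assessment form could mean that baseline serum is tested early. That evidence is weak: the same list on the form contains gut microbiota, whose qPCR is described only under stage 3 (section 2.3.2), so it looks like a general record template. Early testing would also not rescue the paired test, since evaluation would then be tied to assay run.

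**No drift is documented.** This stands. Nothing in the documents shows that any of these analytes changes at -20°C over 15 weeks, or that this temperature is inadequate. The sources cited for the blood procedure are not available here. The table runs from negligible to near-certain depending on an assumed input, so it shows sensitivity and does not demonstrate an error.

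**The randomised control group already protects the trial.** Largely true. The plan includes unpaired comparisons between groups, describes one handling procedure for all participants, and gives no sign that the arms are treated differently. Two limits remain. Shared runs and storage times are presumed and not required. Section 2.3.1 also sets values against fixed national reference points, and a control arm does not protect that classification.

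**Same-run assay keeps the gap.** True: baseline serum must wait for week 15. It removes run differences between a participant's visits but leaves the difference in storage time, so it supports the between-arm analysis and cannot replace it.

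**Conclusion.** The point holds as a limited, conditional one. If serum is assayed in stage 3, as sections 2.3 and 2.3.1 indicate, baseline serum is 14 to 15 weeks older than final serum. If it is tested earlier, run replaces storage as the confounder. In both cases the within-arm paired tests cannot isolate a programme effect on glucose and lipids. For an assumed mean shift of 0.1 to 0.3 SD of change, the false-positive rate would be about 8% to 30% with n=25 and 11% to 55% with n=50; at 0.05 SD it is close to nominal.

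A reader might infer that storage will manufacture a benefit for the programme. The documents do not support that: they give no drift, and loss in storage would work against four of the five hypothesised changes and favour only HDL-C. A reader might also infer that the trial's glucose and lipid results are invalid as a whole. That does not follow either, because drift shared by both arms cancels in the between-arm comparison. The importance is modest, and the reason to act is that the remedy is nearly free.

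**What to change.** 1. In section 2.3.4, state that conclusions on glucose and lipids rest on the between-arm difference in change from baseline, and that within-arm paired tests are descriptive only. This change does most of the work.
2. In section 2.3.1, require that both visits of a participant are assayed in the same run, with both arms balanced in every run. This makes explicit the equal handling on which the cancellation depends.
3. Reconcile sections 2.2.3 and 2.3 with the initial assessment form in Supplementary Material 3 on when baseline serum is tested, and give a maximum storage time.
4. Where capacity allows, keep serum aliquots in the -80 °C storage already planned for stool.

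The cost is a few sentences, a run plan and some freezer space; spare capacity at -80 °C is not stated in the documents and would need checking. No extra samples are needed.
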